4.1.1 Primary Endpoint

- Number of participants with a minimum four-fold increase in post-vaccination HPV-16 and HPV-18 neutralizing antibody titers 30 days after receiving the third and final vaccine dose as determined using an HPV pseudovirus neutralization assay

4.1.2 Secondary Endpoint

1. Number of HPV-specific Bmem at baseline (D0), D30, D180 (Visit 13), Visit 13 + 30±5 days, D365, D730

4.1.3 Exploratory Endpoints

1. Number of GCTfh, GCB, and HPV-specific GCB in fine needle aspirates at D-30 to D0, D14, D30, D60, Visit 8 + 14±5 days, Visit 8 + 30±5 days, D180, Visit 13 + 14±5 days, Visit 13 + 30±5 days.
2.
 - a. Correlation of magnitude of peak GCTfh responses with magnitude and durability of HPV-specific antibody and B cell responses
 - b. Gene expression profile of HPV vaccine-induced GCTfh
 - c. Correlation of GCTfh gene expression profiles with magnitude and durability of HPV-specific antibody and B cell responses
3.
 - a. Correlation of magnitude of GCB with Bmem or PC-precursor phenotype with magnitude, type, and durability of B cell memory induced by 9-valent HPV vaccination
 - b. Gene expression profile of HPV vaccine-induced GCB
 - c. Correlation of GCB gene expression profiles with magnitude, type, and durability of B cell memory induced by 9-valent HPV vaccination
4. Antibody repertoires, gene expression profiles, and monoclonal antibodies from GCB at D-30 to D0, D14, D30, D60, Visit 8 + 14±5 days, Visit 8 + 30±5 days, D180, Visit 13 + 14±5 days, Visit 13 + 30±5 days; Bmem at D0, D14, D30, D60, Visit 8 + 7±1 days, Visit 8 + 14±5 days, Visit 8 + 30±5 days, D180, Visit 13 + 7±1 days, Visit 13 + 14±5 days, Visit 13 + 30±5

Protocol Title: Assessing immunological basis of durable antibody responses to 9-valent HPV vaccination

days, D365, D730, D1095, D1460, D1825; PB at D0, D14, D30, D60, Visit 8 + 7±1 days, Visit 8 + 14±5 days, Visit 8 + 30±5 days and D180, Visit 13 + 7±1 days, Visit 13 + 14±5 days, Visit 13 + 30±5 days; and PC at D730 and D1825.

5. Gene expression changes occurring in blood post-vaccination at D1 (optional visit), D7, Visit 8 +1 day (optional visit), and Visit 8 + 7±1 days relative to baseline (D0, D60).
6. Frequency of PB at D0, D14, D30, D60, Visit 8 + 7±1 days, Visit 8 + 14±5 days, Visit 8 + 30±5 days, D180, Visit 13 + 7±1 days, Visit 13 + 14±5 days, Visit 13 + 30±5 days
7. Number, phenotype, and gene expression profiles of HPV-specific PC at D730 and D1825
8. Titers of binding HPV-specific antibodies and distribution of HPV-specific binding antibody isotypes in saliva at D0, D30, D60, Visit 8 + 30±5 days, D180, Visit 13 + 30±5 days, D365, D730
9. Frequency, phenotype, and gene expression profile of cTfh (total and HPV-specific) and their independent correlations with the magnitude of antibody and PB responses induced by 9-valent HPV vaccination
10. Frequency, function and phenotype of HPV-specific CD4 T cells at D0, D14, D30, D60, Visit 8 + 7±1 days, Visit 8 + 14±5 days, Visit 8 + 30±5 days, D180, Visit 13 + 7±1 days, Visit 13 + 14±5 days, Visit 13 + 30±5 days, D365, D730, D1095, D1460, D1825
11. HPV-specific L1 CD4 T cell epitopes
12. Titers of HPV-specific antibodies collected by microsampler at D0, D30, Visit 8 + 30±5 days, Visit 13 + 30±5 days, D365
13. Titers of binding and neutralizing HPV-specific antibodies and distribution of HPV-specific binding antibody isotypes (e.g., IgA, IgM, IgG) in serum at baseline (D0), D14, D30, D60, Visit 8 + 7±1 days, Visit 8 + 30±5 days, D180, Visit 13 + 7±1 days, Visit 13 + 30±5 days, D365, D730, D1095, D1460, D1825
14. Antibody epitopes of polyclonal antibodies in blood or monoclonal antibodies cloned from B cells at any study visit.

5. Study Intervention/Investigational Agent

5.1 Description

5.1.1 The 9-valent HPV vaccine is manufactured by Merck & Co., Inc. headquartered in Kenilworth, NJ.

The 9-valent HPV vaccine, or Gardasil-9, is a non-infectious recombinant vaccine prepared from the purified virus-like particles (VLPs) of the major capsid (L1) protein of HPV Types 6, 11, 16, 18, 31, 33, 45, 52, and 58. The L1 proteins are produced by separate fermentations using recombinant *Saccharomyces cerevisiae* and self-assembled into VLPs. The fermentation process involves growth of *S. cerevisiae* on chemically-defined fermentation media which include vitamins, amino acids, mineral salts, and carbohydrates. The VLPs are released from the yeast cells by cell disruption and purified by a series of chemical and physical methods. The purified VLPs are adsorbed on preformed aluminum-containing adjuvant (Amorphous

Protocol Title: Assessing immunological basis of durable antibody responses to 9-valent HPV vaccination

Aluminum Hydroxyphosphate Sulfate or AAHS). The 9-valent HPV VLP vaccine is a sterile liquid suspension that is prepared by combining the adsorbed VLPs of each HPV type and additional amounts of the aluminum-containing adjuvant and the final purification buffer.

The 9-valent HPV vaccine, or Gardasil-9, is a sterile suspension for intramuscular administration. Each 0.5-mL dose contains approximately 30 mcg of HPV Type 6 L1 protein, 40 mcg of HPV Type 11 L1 protein, 60 mcg of HPV Type 16 L1 protein, 40 mcg of HPV Type 18 L1 protein, 20 mcg of HPV Type 31 L1 protein, 20 mcg of HPV Type 33 L1 protein, 20 mcg of HPV Type 45 L1 protein, 20 mcg of HPV Type 52 L1 protein, and 20 mcg of HPV Type 58 L1 protein.

Each 0.5-mL dose of the vaccine also contains approximately 500 mcg of aluminum (provided as AAHS), 9.56 mg of sodium chloride, 0.78 mg of L-histidine, 50 mcg of polysorbate 80, 35 mcg of sodium borate, <7 mcg yeast protein, and water for injection. The product does not contain a preservative or antibiotics.

Gardasil-9 is supplied as a 0.5-mL single-dose vial or 0.5-mL single-dose prefilled Luer Lock syringe with tip cap.

After thorough agitation, GARDASIL 9 is a white, cloudy liquid.

The prospective cohort will receive all three doses of the 9-valent HPV vaccine by intramuscular injection as part of the study.

- 5.1.2 When indicated, 1% lidocaine, an FDA approved local anesthetic, will be injected subcutaneously to numb the area of the lymph node being sampled; whereas 1-2% lidocaine will be injected into the tissue surrounding the area where the bone marrow will be removed. In adults the recommended dose is 7 mg/kg with a maximum of 500 mg.
- 5.1.3 When indicated, lorazepam, an FDA-approved benzodiazepine, will be administered as an anxiolytic prior to the bone marrow aspirate procedure per the clinician performing the procedure. Lorazepam will be administered sublingually per manufacturer dosing recommendations.

5.2 Drug/Device Handling

- 5.2.1 After purchase of the 9-valent HPV vaccine, the Hope Clinic Investigational Drug Services will be responsible for storage and disposition of the vaccine. Only IDS staff have the code to the keypad restricting pharmacy access. Logs of receipt, temperature, maintenance, and disposal will be maintained in the study file. The pharmacist will prepare a single dose (0.5 mL) for each participant as described below.

Protocol Title: Assessing immunological basis of durable antibody responses to 9-valent HPV vaccination

Gardasil-9 doses should be stored refrigerated at 2 to 8°C (36 to 46°F). Doses will not be frozen. Doses that are frozen will be discarded. Doses must be protected from light. A dose should be administered as soon as possible after being removed from refrigeration. A dose can be administered provided total (cumulative multiple excursion) time out of refrigeration (at temperatures between 8°C and 25°C) does not exceed 72 hours. Cumulative multiple excursions between 0°C and 2°C are also permitted as long as the total time between 0°C and 2°C does not exceed 72 hours.

All doses will be administered as directed on the package insert (Appendix C). For persons age 15 through 45 years, Gardasil 9 should be administered as a 3-dose regimen, with one dose at 0, 2, and 6 months. The first dose will be given at the initial study visit after informed consent is obtained.

Doses should not be diluted or mixed with other vaccines. Each dose should be shaken well before use to maintain suspension of the vaccine. After thorough agitation, Gardasil-9 is a white cloudy liquid. Doses should be inspected visually for particulate matter and discoloration prior to administration, whenever solution and container permit. A dose should be discarded if particulates are present or if it appears discolored.

Each dose should be administered intramuscularly in the deltoid.

Patients should be observed for 15 minutes after administration.

For single-dose vial use, the 0.5-mL dose of vaccine should be shaken well before use, drawn from the single-dose vial using a sterile needle and syringe, and used promptly. Vial will be discarded after use.

- 5.2.2 Lidocaine 1% will be injected intra-dermally and subcutaneously to the margin of the lymph node to be sampled to numb the area. Lidocaine 1-2% will be injected into the tissue surrounding the area where the bone marrow will be removed to confer local anesthesia.
- 5.2.3 Lorazepam will be administered sublingually per manufacturer dosing recommendations.

6. Procedures Involved

Study Design

The study is designed to better understand how the 9-valent HPV vaccine elicits such potent and durable antibody responses in humans. In this study we also propose to compare the diversity, SHM levels, and affinity of antigen-specific B cell and PC repertoires using the HPV vaccine as a model.

This is a single center, longitudinal cohort study in which participants will receive 9-valent HPV vaccine according to package insert (i.e., one dose of 9-valent HPV vaccine on day (D) 0

Protocol Title: Assessing immunological basis of durable antibody responses to 9-valent HPV vaccination

followed by a second dose 2 months later and a third dose 6 months later). Participants enrolled in the study will be asked to donate biological samples such as blood, saliva, and will undergo fine needle aspiration procedure for axillary lymph node and bone marrow sampling. Immune responses in the blood, saliva, bone marrow, and lymph nodes will be assessed in participants receiving the HPV vaccine.

Blood samples for immunologic testing will be collected at screening (from D-60 to D-45), on D0 (before vaccination), D1 (optional visit), D7, D14, D30, D60 (before vaccination), Visit 8 +1 day (optional visit), Visit 8 + 7±1 days, Visit 8 + 14±5 days, Visit 8 + 30±5 days, D180 (before vaccination), Visit 13 + 7±1 days, Visit 13 + 14±5 days, Visit 13 + 30±5 days, D365, D730, D1095, D1460, D1825. Saliva samples for antibody testing will be collected on D0 (before vaccination), D30, D60 (before vaccination), Visit 8 + 30±5 days, D180 (before vaccination), Visit 13 + 30±5 days, D365, and D730.

Axillary lymph node sampling by fine needle aspiration will be done 3 times per group. Group 1 will have lymph node sampling done D-30 to D0, D14, and D30. Group 2 will have lymph node sampling done D60, Visit 8 + 14±5 days, and Visit 8 + 30±5 days. Group 3 will have lymph node sampling D180, Visit 13 + 14±5 days, and Visit 13 + 30±5 days. Bone marrow sampling will be done for all groups at D730 and D1825.

The study plans to enroll 16 healthy adults between the ages of 18 to 45 years. In order to reach the sample size 16, we will enroll 32 participants to account for screen fails. However, the enrollment number may expand depending on the scientific questions being pursued at any given time. The donated samples will be stored and processed in Emory Infectious Diseases Laboratory at the Hope Clinic.

6.1 Schedule of Procedures (please see Appendix A)

6.2 Screening and Consenting

6.2.1 Participants responding to study ads will contact the Hope Clinic for a telephone screening where the research study will be explained in lay terms and eligibility criteria of the participant will be reviewed (see sections 10.1 and 10.2). If the participant is found to be eligible and continues to be interested in participating after reading the informed consent (emailed or mailed to him/her/them), an in person screening appointment will be scheduled (Day(D)-60 to D-45).

The call will last up to 30 minutes.

6.2.2 At the in person screening appointment, study staff will review the informed consent form with the participant and will answer all questions related to the study.

- Once the participant signs the informed consent, he/she/they will be assigned a unique study participation number.
- The volunteer will be asked to provide demographic information (birthdate, age, sex/gender, race and/or ethnicity) and information related to his/her/their medical history, including current medication use and vaccination history (have they ever received an HPV vaccine) and sexual history (number of partners with which they have had sexual intercourse (penetrative sex) and any history of genital warts, an abnormal pap smear, or positive HPV DNA test).
- The participant's vital signs and medical history will be recorded, including current medication use and vaccination history, and a targeted physical exam will be conducted as indicated, based on review of the participant's health status.
- All participants will have blood drawn for immunological screening tests.
- In preparation for saliva collection at the first vaccine visit, participants are notified to avoid eating for at least 30 minutes prior to sample donation. The participant should rinse their mouth after the most recent meal by drinking or gargling water. They may continue to take water up until 30 min prior to sample donation.
- Safety labs (WBC, hemoglobin, platelets, PT, PTT) will be conducted at this visit unless available by medical records.

This visit will last approximately 90-120 minutes.

The duration of participation for each participant is approximately 27 months.

6.2.3 Immunological screening test results will be available approximately two weeks after blood draw. If immunological screening tests reveal that participant has HPV 6, 11, 16, 18, 31, 33, 45, 52 or 58-specific binding antibodies (above the laboratory established cut-off value based on results from children's serum and lower limits of quantification), the participant will be screen failed. Only participants that screen pass will be contacted to continue the study. Laboratory results of the HPV binding antibody assay or other serologic assays will not be provided to the participant because the assays are not FDA-approved and "research only" test results cannot be reported out to patients as per federal CLIA regulations. Safety labs will be reviewed by a licensed clinician/co-investigator who will assess them for contraindications to planned procedures (lab result grade 2 or greater). Safety labs results will be shared with participant by phone prior to setting up the next appointment. Safety labs can be repeated at investigator discretion.

6.3 FNA Procedure (D-30 to D0 and other time points)

Protocol Title: Assessing immunological basis of durable antibody responses to 9-valent HPV vaccination

- Study personnel will first review the participant's current health status and note any changes in medical history since the screening visit, including medication use and vaccination history.
- The participant's vital signs will be recorded.
- For female volunteers of childbearing potential, a urine pregnancy test will be performed. Only females with a negative urine pregnancy test will get the procedure.
- Inclusion/exclusion criteria will be also verified before procedure.
- Participant will have blood drawn for immunological assays and saliva collected for antibody assays on days indicated in Schedule of Procedures (Appendix A).
- Participant will undergo lymph node sampling:
 - Group 1: Participants will undergo an FNA at D-30 to D0. Participants will repeat the procedure at D14±5 and D30±5.
 - Group 2: Participants will undergo an FNA on the same day, but prior to, the second vaccine dose (D60±5) or up to 5 days before. Participants will repeat the procedure at Visit 8 + 14±5 days and Visit 8 + 30±5 days.
 - Group 3: Participants will undergo an FNA on the same day, but prior to, the third vaccine dose (D180±5) or up to 5 days before. Participants will repeat the procedure at Visit 13 + 14±5 days and Visit 13 + 30±5 days.

Tissue sampling of an axillary lymph node will be carried out percutaneously. The FNA procedure involves performing a pre- procedure “time out” with the team and participant present to confirm identity of the participant and the nature of the procedure. Both axillae will be scanned with ultrasound to identify the most accessible node for biopsy. Once this has been identified, the skin will be steriley prepared, and lidocaine 1%, an FDA-approved local anesthetic, will be injected intra-dermally and subcutaneously to the margin of the node in question to numb the area. A small skin incision will be made. Under real-time sonographic guidance, a 21-gauge needle will be placed. Two to four passes will be made to retrieve cytologic material. After tissue is retrieved, manual pressure will be applied to the biopsy site for 5-10 minutes. The technologist will review post-procedure instructions with the participant. The incision site will be steriley dressed and the participant will be released after vital signs are checked.

At the end of the visit, the participant will also be instructed to promptly call the site if he/she/they develop any complication from the lymph node sampling. Participants calling the site will receive further instructions on the

proper course of action, including a return to the clinic for immediate evaluation, if appropriate.

This visit will last approximately 120 minutes.

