Sample Size	8 female and 8 male participants split into 3 groups (Group 1 = 8 participants, Group 2 = 4 participants; Group 3 = 4 participants; with equal numbers female and male participants per group)
Study Duration for individual participants	Approximately 1892 days (~63 months)
Study Specific Abbreviations/ Definitions	
HPV – human papillomavirus
 
GCTfh – germinal center T follicular helper cells
 
cTfh – circulating T follicular helper cell
 
Bmem – memory B cell
 
PC – plasma cell (bone marrow)
 
PB – plasmablast (circulating)

Funding Source (if any)	Departmental Funding

2. Objectives

Specific aims

1. Determine if 9-valent HPV vaccination induces germinal centers in humans. We hypothesize that the HPV vaccine generates germinal centers as these structures are important for the formation of Bmem and we have previously shown that the 4-valent HPV vaccine elicits Bmem^{1,2}.
2. To determine if the magnitude or quality of GCTfh responses correlates with the durability of Ab and B cell responses induced by 9-valent HPV vaccination. We hypothesize that the quality of GCTfh will be a better predictor of Ab durability than GCTfh magnitude.
3. To assess correlations between the phenotype of GCB and the magnitude, type, and durability of B cell memory induced by 9-valent HPV vaccination. We hypothesize that we will observe more PC precursors than Bmem precursors in the germinal center given

that HPV Bmem rapidly wane to near baseline levels, whereas antibody levels are high and stable (suggesting potent and durable PC responses).

4. To compare B cell Ab repertoires and gene expression profiles of HPV-specific Bmem, GCB, and PC following 9-valent HPV vaccination. Previous work in mice suggests that Bmem repertoires are less somatically mutated and harbor more breadth than PC repertoires, which is what we expect to observe in our comparison here. However, we have also found that human anti-HPV Abs require little somatic hypermutation to potently neutralize HPV and thus we may find that fewer differences between these repertoires in the case of HPV.

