Most vaccines protect by generating antibodies. However, how this benchmark subunit vaccine – let alone any vaccine – elicits durable antibodies and Bmem is not understood. Is it dependent on antigen valency/avidity, given that the HPV vaccine antigen (L1) spontaneously assembles into virus like particles with 72 L1 subunits? Or is it due to trace amounts of DNA in the vaccine, which could provide B cell co-stimulation through pattern recognition receptors (e.g., TLR9) on B cells or other antigen-presenting cells (e.g., macrophages or dendritic cells)? Or does the vaccine induce and require GCTfh, which are critical to the formation of Bmem and long-lived PC? Further studies into how vaccines elicit potent, durable antibody responses will aid our ability to successfully and reliably design subunit vaccines that recapitulate these highly desired antibody responses.

Therefore, we designed this study to better understand how the 9-valent HPV vaccine elicits such potent and durable antibody responses in humans. We hypothesize that the HPV vaccine induces germinal center formation and propose to test this hypothesis by evaluating fine needle aspirates for the presence of GCTfh or GCB, which correlate with germinal center formation assessed by more comprehensive, albeit more invasive, methods (e.g., lymph node biopsy and immunohistology)^{23,24}. We also propose to measure HPV-specific GCB. In measuring GCB, we propose to assess the fraction of Bmem and PC precursors and how these numbers correlate with the magnitude and durability of Bmem responses and magnitude and durability of PC and antibody responses. We also propose to assess the gene expression profiles of single GCTfh and GCB cells to learn, for example, whether genes associated with B cell help (IL-21) or specific pattern recognition receptor pathways (TLR9) are upregulated in these cells. We also propose to examine the gene expression changes in blood activated by the first and second dose of this vaccine relative to baseline. These analyses will enable us to study associations between the innate immune activation and GC magnitude and between GCTfh or GCB gene expression profiles and the magnitude and durability of the antibody, PC, and Bmem responses. Moreover, these analyses will establish important benchmarks for future studies aimed at understanding the durability of immunity for candidate vaccines or natural infections (e.g., SARS-CoV-2).

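### In Group 2 at dose 2, and possibly Group 1 at dose 1, blood gene expression change cannot separate the vaccine from a lymph node aspirate done before the dose

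*Protocol*

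**What the plan says.** Section 4.1.3, item 5 defines the endpoint as "Gene expression changes occurring in blood post-vaccination at D1 (optional visit), D7" and at the matching visits after dose 2, each against the pre-dose draw (D0 or D60). Specific aim 5 (section 2) and the Background (section 3) describe these changes as activated by the vaccine. Section 17.1 states that there is no placebo control.

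Section 6.3 places an aspirate before these baselines in two groups. For Group 1: "Participants will undergo an FNA at D-30 to D0". For Group 2: "Participants will undergo an FNA on the same day, but prior to, the second vaccine dose (D60±5) or up to 5 days before". The procedure involves lidocaine, a small skin incision and two to four needle passes.

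Section 1 gives the group sizes: "Group 1 = 8 participants, Group 2 = 4 participants; Group 3 = 4 participants". Appendix A schedules transcriptomic blood without restriction by group. Section 6.4 puts blood before vaccine. Section 6.3 lists blood ahead of the aspirate but does not say that this order is required.

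The Background also plans to "study associations between the innate immune activation and GC magnitude". It does not say which participants or which dose pairing will be used.

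**The concern.** A change from baseline with no control group can be credited to the vaccine only if nothing else happened around baseline. In Group 2 something else always does: an invasive procedure in the five days up to dose 2. In Group 1 it may. The protocol does not mention the aspirate as a possible cause of blood gene expression change, although section 14.6.1 recognizes that other exposures could affect the innate and adaptive assays.

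At stake is attribution. A response to the procedure could be reported as innate activation by the vaccine, or could raise the baseline and hide such activation. The association with germinal center size is the more exposed use, because post-dose lymph node data come only from people who also had a pre-dose aspirate.

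**Working it through.** The protocol gives no figure to reproduce. The check uses group sizes (section 1), visit windows (sections 6.3 and 6.5, Appendix A) and the endpoint's draws (section 4.1.3).

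**1. Days from the pre-dose aspirate to each draw**

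| | Baseline | Next day (optional visit) | Day 7±1 |
|---|---|---|---|
| Group 1, dose 1 | 0–30 | 1–31 | 6–38 |
| Group 2, dose 2 | 0–5 | 1–6 | 6–13 |

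The first post-dose aspirate is at day 14−5 = 9 at the earliest, after the last possible day-7 draw (7+1 = 8). Within a dose, only the pre-dose aspirate can interfere.

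**2. Who is unexposed**
- Dose 1: Groups 2 and 3, 4+4 = 8, with no aspirate yet.
- Dose 2, outside Group 2: Groups 1 and 3, 8+4 = 12. Group 1's last aspirate (D30±5) is 55−35 = 20 to 65−25 = 40 days before the D60±5 baseline. Only Group 3 (n=4) has had none.

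**3. Direction**
Let s0 and s1 be the aspirate's contribution at the baseline and post-dose draws. The measured change shifts by b = s1 − s0. If the tube precedes a same-day aspirate, s0 = 0 and b = s1. If the aspirate was days earlier and its effect is fading, s0 exceeds s1 in size and b has the opposite sign. The documents fix neither s0 nor s1.

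**4. Size in the all-participant mean**
Assume all attend and every exposed person shifts by b.
- Dose 1: (8/16)b = 0.5b, the upper limit, since some Group 1 aspirates may be weeks before D0.
- Dose 2: (4/16)b = 0.25b.

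For an assumed b of 0.25 to 1 SD, the shift is 0.125–0.5 SD at dose 1 and 0.06–0.25 SD at dose 2. In the exposed group alone it is the full b.

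**5. Same-dose pairing with germinal center data**
Post-dose-1 lymph node data exist only for Group 1, and post-dose-2 data only for Group 2. So 8/8 and 4/4 had a pre-dose aspirate. A constant shift would not change a correlation, but a shift that varies with the interval would become part of the predictor. An interval covariate is not workable in Group 2: intercept, innate score and interval leave 4−3 = 1 residual degree of freedom.

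**6. What the unexposed groups can deliver**
Standard error relative to all 16, with equal variance:
- Groups 2+3 at dose 1: √(16/8) = 1.41
- Groups 1+3 at dose 2: √(16/12) = 1.15
- Group 3 alone at dose 2: √(16/4) = 2.0

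Detectable exposed-versus-unexposed difference, assuming two-sided 0.05 and 80% power (normal approximation 2.80·√(1/n1+1/n2); noncentral t in brackets):
- Dose 1, 8 v 8: 1.40 SD (1.51)
- Dose 2, 4 v 12: 1.62 SD (1.74)
- Dose 2, Group 2 v Group 3, 4 v 4: 1.98 SD (2.38)

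Agreement between groups would therefore not rule out a moderate aspirate effect.

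**The case against.** The strongest reply is that nothing in the protocol shows that a fine needle aspirate changes blood gene expression. Section 14.3.4 says the procedure is generally well tolerated, with 8 of 13 reporting no to mild discomfort. The endpoint is one of 14 exploratory items, section 17.1 promises only descriptive data, no section says all 16 will be pooled, and analysis sets can be left to an analysis plan. This stands as a limit on importance. It does not remove the confounding, because the protocol names the vaccine as the cause and has no control for the procedure.

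Second, blood before aspirate is already the listed order in section 6.3. That is so, and that order does not keep a same-day aspirate out of the next-day sample. It only makes the baseline comparable among same-day cases.

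Third, using only unexposed groups would largely lose the within-person comparison of doses: Groups 2+3 and Groups 1+3 share only Group 3 (n=4). This stands, and is why the all-participant estimate should stay.

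Some stronger readings are tempting but unsupported:
- That Group 1's aspirate is always close to D0. It may be a month earlier.
- That Groups 1 and 3 are both free of aspirates at dose 2. Group 1 has had three by then, the last 20–40 days before.
- That the innate–germinal center association uses exactly the exposed people. The Background phrase does not define the pairing, and dose-1 innate data from Groups 2 and 3 could be related to their later lymph node data.

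**Conclusion.** The point holds as a minor one. By design, Group 2 (4 of 16) always has an aspirate 0–5 days before the dose-2 baseline, and Group 1 (8 of 16) may have one anywhere from 30 days before D0 to D0 itself. In those participants endpoint 5 cannot separate procedure from vaccine. Any shift b enters the all-participant mean as 0.25b at dose 2 and at most 0.5b at dose 1, assuming full attendance; the draws nearest the aspirate are optional, so actual shares may differ.

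A reader might infer that the gene expression results are biased by a known amount or in a known direction. The documents do not support that: whether b differs from zero, and its sign, are assumptions. For the innate–germinal center association, the absence of anyone without a pre-dose aspirate applies only if same-dose pairing is used. The primary and secondary endpoints are unaffected.

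**What to change.** In endpoint 5, keep the all-participant estimate and add results by aspirate exposure:
- Dose 1: show Groups 2+3 (n=8, no prior aspirate) separately from Group 1, and list each Group 1 participant's aspirate-to-D0 interval.
- Dose 2: show the estimate without Group 2 (Groups 1+3, n=12), noting that Group 1's last aspirate was 20–40 days earlier. Show Group 3 alone (n=4, no aspirate yet) and Group 2 separately.

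State that on days with both, the transcriptomic tube is drawn before the aspirate. Derive the aspirate-to-draw interval from visit dates, checking that an aspirate done before Visit 8 carries its own date. Use the interval for description, not as a model covariate. State that a same-dose innate–germinal center association cannot separate aspirate from vaccine effect.

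This needs wording changes and no new samples. The cost is precision: standard errors are about 1.4 times (dose 1), 1.15 times (Groups 1+3, dose 2) and 2 times (Group 3 alone) those with all 16. Agreement between groups should not be presented as proof that the aspirate has no effect.
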